5.2 Secondary Outcomes

- 5.2.1 Since the first secondary objective is to examine metabolic and microbial signatures are two time points (pre- and post- surgery) therefore the following outcomes will be gathered to examine this:
 - 5.2.1.1 Quantitative assessments of metabolic characteristics measured at pre-surgery
 - 5.2.1.2 Quantitative assessments of microbial assessments measured at pre-surgery
 - 5.2.1.3 Quantitative assessments of metabolic characteristics measured at post-surgery
 - 5.2.1.4 Quantitative assessments of microbial assessments measured at post-surgeryUsing these four sets of quantitative assessments, “signatures” will be developed (described in statistical analysis section) and compared to see whether there are characteristics that remain similar or change when comparing pre- and post-surgical measures.
- 5.2.2 Patient LC Stage will be gathered as a secondary outcome. This outcome will be used with the outcome measures gathered for primary outcome 5.1.2 (described above) to address the secondary objective (To identify signatures which are associated with LC stage).
- 5.2.3 Patient pulmonary function status (assessed by [name]) will be gathered as a secondary outcome. This outcome will be used with the outcome measures gathered for primary outcome 5.1.2 (described above) to address the secondary objective (To identify signatures which are impacted by patient’s pulmonary function status).

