6.0 Analytic Plan

6.1 Sample Size and Power

This is a pilot study therefore; many of the objectives are exploratory in nature. With this in mind, we plan to recruit two cohorts of patients with this study, 45 female and 45 males. In order to be able to examine the questions concerning the possible relationships of metabolic and microbial signatures over time and with lung cancer outcomes, both pre- and post- surgery measures are needed. Therefore, each patient must provide both a pre- and post-surgery sample (optional blood will be allowed) in order to be used in the signature analyses. If a post collection is not performed or collection is unsatisfactory, the patient will be replaced. Therefore, our target sample size of 90 patients (45 male/45 female) is the target for patients with both pre- and post- samples collected.

Pilot Study: Metabolic and microbial profiling of lung cancer
Wake Forest Baptist Comprehensive Cancer Center (WFBCCC)
WFBCCC # 03219

First, for the primary objective of assessing feasibility, we can determine the total number of patients needed in order to enroll 90 patients. To examine this question we will determine 1) the number of patients screened for the trial, 2) among those screened, the number who are eligible, 3) among those eligible, the number who consent to participate, 4) among those who participate, the number who provide pre-surgery samples, and 5) among those who provide pre-surgery samples, the number who provide post-surgery samples. Based on our design we will enroll patients until 90 provide pre- and post- surgery samples.

Since we do not know prospectively how many patients will be needed to enroll 90 we will conservatively estimate several possible scenarios and for each scenario describe the width of the corresponding 95% Exact Clopper Pearson confidence interval for proportions.

The table below shows different total number of patients needed to enroll 90 for the study, beginning with 120 (75% enrollment rate) to 180 (50% enrollment rate).

# screened and eligible	Number enrolled	Enrollment rate	Lower 95% limit	Upper 95% limit
120	90	75%	0.66	0.82
150	90	60%	0.52	0.68
180	90	50%	0.42	0.58

As can be seen from the above, the confidence intervals for each scenario are approximately +/- 10% or less depending on the scenario observed.

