For the other primary outcomes, metabolic and microbial assessments taken at two time points (pre- and post- surgery), we can determine statistical power in several ways. One straight-forward approach will be to assess the difference in biomarkers (metabolic or microbial) that can be detected when comparing pre- and post- surgical assessments within patients. If there are 90 patients then there is 80% power (using an alpha=0.05, 2-sided) to detect a difference in a biomarker measure equal to 0.30 standard deviations for that marker.

Since this is a pilot study, the above power calculations suggest that useful data concerning feasibility and effect size assessments for biomarkers can be determined in this study. Multiple comparison adjustments are not considered at this time since the focus of examining these effect size estimates is to determine an overall ranking of measures, in order to inform future studies concerning which signatures may be most promising to examine further.

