6.3 Analysis of Secondary Outcomes

For the analysis of metabolic and microbial measures we will examine each marker assessed both at pre- and post- surgery. We hypothesize that markers that are associated with lung cancer will change between the pre- and post- surgery setting, whereas markers that are independent of lung cancer will not change between the two time points. Therefore, a first analysis will be to examine

Pilot Study: Metabolic and microbial profiling of lung cancer
Wake Forest Baptist Comprehensive Cancer Center (WFBCCC)
WFBCCC # 03219

a series of paired t-tests to determine which markers significantly change between the two time points for patients.

In addition to this analysis, we wish to determine whether there are any marker signatures that appear in groups of patients. To do this we will use cluster analysis methods to determine whether there are any groups of patients who share similar marker profiles pre-, post- or change from pre- to post- for metabolic and microbial measures. If we are able to identify clusters of patients with common marker signatures, we will then determine whether there are other disease characteristics that are shared by these patients (i.e., tumor stage, lung function, etc.). This analysis approach will also be used below to address the analysis of secondary outcomes. As stated above, this is a pilot study, therefore these cluster analyses will be considered exploratory and hypothesis generating.

To address the two secondary objectives, we will use the same data gathered for the primary objective as described above, however we will compare those data to the two secondary outcomes measures (LC Stage and patient pulmonary function). The analytic difference between these two measures is that LC stage will be an ordinal variable and pulmonary function is a continuous measure.

For LC Stage, we will examine whether pre-surgery, post-surgery or change from pre- to post-surgery metabolic or microbial measures are different depending on LC Stage. To do this we can consider the metabolic or microbial measures as outcomes and use a general linear models framework to see if LC Stage (included as a class variable, but then examined as an ordinal variable using a contrast statement in GLM) is associated with any marker.

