In addition to this analysis where individual markers are considered separately, we will use cluster analyses (as described above) based on the marker data and then determine whether there are associations between cluster membership and LC Stage using 2-way contingency tables.

For pulmonary function, we will use the same approach as for LC Stage, except that pulmonary function will be considered as a continuous variable in the model. Thus, we can examine associations (correlations) between the marker measures and pulmonary function. In addition, pulmonary function can be examined at both time-points (pre- and post- surgery) thus we can examine the relationships between pulmonary function measures and biomarker measures at each time points (and the change in measures over time).

In addition to these analyses, additional exploratory analyses will be examined to determine whether other patient level characteristics (i.e., gender, age, smoking history (current/former/never), etc.) are associated with different metabolic and/or microbial signatures or measures in a general linear model framework.

Since this is a pilot study and the sample size is moderate ($n=90$), these additional analyses will be primarily hypothesis generating to allow us to determine whether there are potential signals in the data that may need to be further examined in larger trials.

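### Section 6.3 names no covariates for the pulmonary-function and stage marker models, so smoking, and possibly sex and age, can pass into those estimates

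*Combined protocol and SAP*

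**What the plan says.** Section 6.3 treats each metabolic or microbial marker as an outcome and proposes to "use a general linear models framework to see if LC Stage" is associated with it, entering stage as a class variable with an ordinal contrast. Pulmonary function gets the same treatment but as a continuous term: "Thus, we can examine associations (correlations) between the marker measures and pulmonary function". Each analysis is planned for pre-surgery values, post-surgery values and change. No other term is named in either model.

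Sex, age and smoking enter one step later, in additional exploratory analyses asking whether "other patient level characteristics (i.e., gender, age, smoking history (current/former/never), etc.) are associated with different metabolic and/or microbial signatures". There they are tested as predictors in their own right. Nothing says they enter together with stage or pulmonary function.

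Two other places bear on this:

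- Section 4.2.1 collects medication, food and tobacco data at both visits because they may confound the metabolic and microbial signatures. Section 6 gives no rule for using them as adjusters.
- Section 6.1 makes sex a design factor: "we plan to recruit two cohorts of patients with this study, 45 female and 45 males".

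**The concern.** Suppose a factor shifts both lung function and a marker. The unadjusted slope of marker on lung function then picks up that shared influence even when the two have no direct link. A separate model showing that the marker varies with smoking alerts the reader but leaves the slope unchanged.

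Objective 2.2.3 seeks signatures affected by pulmonary function, and section 6.1 says the effect sizes will be used to rank measures for future studies. A ranking built on unadjusted estimates can favour markers of smoking over markers of lung function. Confounding is systematic, so a larger follow-up study analysed the same way would not correct it.

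**Working it through.** **The plan's own figure.** Section 6.1 gives 80% power for the within-patient pre/post comparison at a standardised difference of 0.30 SD: "If there are 90 patients then there is 80% power (using an alpha=0.05, 2-sided"). For a paired t-test the noncentrality is 0.30 × √90 = 2.846 on 89 degrees of freedom, which gives 80.4% power (81.2% by the normal approximation). The figure reproduces. It covers only the pre/post comparison; no power or effect size is given for the stage or pulmonary-function models.

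**Inputs from the documents.** n = 90, since "our target sample size of 90 patients (45 male/45 female) is the target for patients with both pre- and post- samples collected"; alpha 0.05 two-sided, carried over from the pre/post calculation.

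**Inputs assumed.** The size of any smoking or sex effect on lung function or on markers. The documents give none.

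**Method.** Let a binary factor have prevalence p. Let it shift lung function by d₁ and the marker by d₂, both in within-group SDs, with no link between the two inside groups. With k = p(1 − p), the size of the induced correlation is

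r = k·d₁·d₂ / √[(1 + k·d₁²)(1 + k·d₂²)].

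By Fisher's transformation the test statistic is centred at m = atanh(r) × √(90 − 3), where √87 = 9.327. The nominal rejection rate is P(Z > 1.96 − m) + P(Z < −1.96 − m).

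**Smoking** (p = 0.30, k = 0.21, d₁ = 0.5):

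- d₂ = 1.0: r = 0.105 / √(1.0525 × 1.21) = 0.093; m = 0.870; rate 14%.
- d₂ = 1.5: r = 0.1575 / √(1.0525 × 1.4725) = 0.127; m = 1.186; rate 22%.

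Simulation of the same two settings gives 14% and 22% unadjusted, and about 5% with smoking in the model.

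**Sex, only if lung function is in litres** (p = 0.50, k = 0.25, assumed within-sex SD 0.6 L):

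- 0.4 L and 0.3 SD: r = 0.047; rate 7%.
- 0.6 L and 0.8 SD: r = 0.2 / √(1.25 × 1.16) = 0.166; rate 35%.
- 0.8 L and 1.0 SD: r = 0.248; rate 66% by the formula, 68% by simulation.

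With sex in the model the rate is about 5%. On a sex- and age-standardised scale such as percent predicted, d₁ for sex is close to zero and this inflation largely disappears. Smoking is not removed by that scale.

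**No link to the exposure, no inflation.** In simulations where the factor was unrelated to lung function, the unadjusted rate stayed at about 5% however strongly the factor affected the marker. The same logic governs stage: age or smoking must differ by stage before the stage contrast is biased.

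**Change scores.** If a factor adds the same amount to the marker at both visits, it cancels in the difference. The rates above therefore describe the pre-surgery and post-surgery models. An effect of smoking that alters between visits would not cancel.

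**Effect on a ranking.** Among 100 independent null markers with n = 90, the largest |r| is typically about 0.28; among 1,000 it is about 0.35. For one null marker the chance of exceeding 0.28 is 0.7% (atanh(0.28) × 9.327 = 2.683). For a marker carrying the smoking shift it is P(Z > 2.683 − 0.870) = 3.5% to P(Z > 2.683 − 1.186) = 6.7%, about 5 to 9 times as likely.

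**The case against.** The strongest case on the other side has five parts.

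- **The text is silent rather than exclusionary.** A general linear model can take covariates. A reader might infer that the plan rules out adjustment; it does not. The accurate statement is that none is specified.
- **The stage case is not shown.** A reader might infer that sex, age and smoking distort the stage results as they do those for lung function. Nothing in the documents links these factors to stage, and no size is calculated here. This stands, so stage is included in the fix only for consistency.
- **The large figures depend on litres.** A reader might take the 7% to roughly two-thirds range for sex as the expected error. Section 4.2.1 refers only to standard studies under American Thoracic Society recommendations, and section 5.2.3 says "Patient pulmonary function status (assessed by [name]) will be gathered as a secondary outcome" without naming a measure or unit. The litres range is conditional and cannot be the headline. Defining the variable is a separate gap.
- **The aim is ranking, not testing at 5%.** Section 6.1 declines multiplicity adjustment for that reason, and chance alone produces top correlations above those induced here. So it would be too strong to say that every smoking-related marker will be carried forward. The weaker point survives: such markers are over-represented near the top.
- **Pilot status and the separate models.** The primary objective is feasibility, which is unaffected. Markers that track smoking or sex would be visible in the exploratory analyses. This lowers the severity but does not adjust the estimates being ranked.

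**Conclusion.** The concern holds as a specification gap, clearest for the cross-sectional pulmonary-function models. For markers that carry the assumed smoking shift, about 14% to 22% would be nominally associated with lung function without any direct link, against about 5% when adjusted. That is a rate among such markers, not among all markers measured. It rests on assumed values for smoking prevalence and for both smoking effects; weaker effects bring it back towards 5%.

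Sex contributes materially only on a litres scale. For stage, bias is possible but not demonstrated. Analyses of change are protected against additive, time-constant effects. No stated figure in the plan is wrong. Severity is low to moderate, because these are exploratory secondary analyses in a feasibility pilot; the case for acting is that the improvement is nearly free.

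**What to change.** In section 6.3, fit the pulmonary-function models, and for consistency the stage models, with sex, age and baseline smoking (current/former/never) as covariates. Report adjusted estimates beside unadjusted ones, and base the ranking of pulmonary-function and stage signatures on the adjusted estimates. Fix the covariate set before the marker data are analysed.

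The cost is a few sentences. Age and tobacco use are collected under section 4.2.1, and sex is on the registration form in Appendix B. The covariates use 1 (sex) + 1 (age) + 2 (smoking) = 4 degrees of freedom, leaving 84 of the 90 − 2 = 88 residual degrees of freedom in the pulmonary-function model. If the covariates explained nothing, the standard error would rise by roughly √(88/84) = 1.024, or about 2%. It would rise somewhat more where the covariates are correlated with lung function, which is where adjustment is needed.

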4.2 Experimental or Data Collection Methods

4.2.1 Clinical data collection:

All patients will be recruited within the Wake Forest Medical Center.

Medical history will be obtained from the patients charts to identify demographics (age, race, ethnicity, zip code), oncologic history (date of diagnosis and cancer type), and medical history of disease. Pulmonary function tests (PFTs) will be performed by Wake Forest Baptist Health Pulmonary Function Lab as a standard of care for pre-surgical assessment. PFTs will be accepted from other certified laboratories within six months of their appointment. Pulmonary function is

Pilot Study: Metabolic and microbial profiling of lung cancer
Wake Forest Baptist Comprehensive Cancer Center (WFBCCC)
WFBCCC # 03219

defined by undergoing standard pulmonary function studies per American Thoracic Society recommendations. The collection of these pulmonary function studies is often done as part of the pre-surgical assessment collected by a cardiothoracic surgical team. Also, the collection of pulmonary functions studies can help with the classification and treatment of underlying obstructive lung disease that can be crucial to post-operative management.

At pre- and post- surgery, the research nurse will obtain current medications, food/ingestion survey and tobacco use information. This information will be necessary to identify any exogenous factors confounding both metabolic and microbial signatures. Following surgery, information from the patient's final pathology report will be obtained to provide information on the tumor site location, characteristics of the cancer removed, and stage of the cancer.

4.2.2 Non-invasive sample collections:

Pre-surgery follow-up collection: During the patient's surgery consultation meeting with [name], Upon entering the are the patient will be given a receptacle for collection of a urine specimen. Given that blood collection may be seen as invasive to the patient, the patient will be prompted for a blood sample. If the patient agrees, the research nurse will collect 1 redtop vacutainer serum tube and 1 purple top blood tube from the patient. We will then initiate the saliva and exhaled breath volatiles (EBV) and

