will utilize the R-tube collection device (Respiratory Research Inc.) (Figure 3). The R-tube is a one-time use apparatus that utilizes a metal cooling sleeve, placed over the plastic tube, to cool the patient's breath, creating condensation build up within the device. The patient will breathe through the mouth piece for 10 min. Following the collection, a metal plunger will be used to consolidate the condensate within the collection tube and the EBC sample can be transferred to a fresh sterile tube. The saliva, urine and blood tube will be transported to the research lab at room temperature and processed within two hours. All biofluids will be aliquoted, frozen and stored at -80° C until analysis.

Surgical tumor removal: In addition to our non-invasive collections, as part of the Advanced Tumor Bank protocol, the tumor tissue will be collected and banked. We will obtain tumor tissue samples from the Advanced Tumor Bank following processing.

Post-surgery follow-up collection: 24-48 hours prior to their 4-week in-clinic follow-up appointment, patients will be called to remind them for their 4-week follow-up, and follow-up collections will be performed in [name] clinic, 4th floor of the Cancer Center. Upon entering the clinic, the patient will be taken the research nurse visit room. The research nurse will obtain current medications and tobacco use information. The patient will be prompted for a urine sample. If the patient again agrees to a blood sample, the research nurse will collect 1 redtop vacutainer serum tube and 1 purpletop vacutainer EDTA tube from the patient. We will initiate the saliva and exhaled breath collection as described above. Following all of the collections, the patient will be given their incentives for participating in the study.

All samples collected from this study will be banked and will have the potential to be used for future scientific experimentation, which may include additional genetic, proteomic, and metabolomic analyses not described in the data collection section below.

Research Data Collection:

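### Tobacco use is recorded before and after surgery as a possible confounder, but Section 6.3 never uses a change in smoking, so tobacco-sensitive markers could be ranked as lung-cancer markers.

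*Combined protocol and SAP*

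**What the plan says.** **Collection.** Section 4.2.1 states: "At pre- and post- surgery, the research nurse will obtain current medications, food/ingestion survey and tobacco use information". It gives the reason: "This information will be necessary to identify any exogenous factors confounding both metabolic and microbial signatures". The post-surgery paragraph of Section 4.2.2 repeats the tobacco item for the 4-week visit: "The research nurse will obtain current medications and tobacco use information". The activity table in Section 4.3 marks smoking status at both collections, and Section 7.0 lists a tobacco use form.

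**Analysis.** Section 6.3 sets out the working hypothesis that "markers that are associated with lung cancer will change between the pre- and post- surgery setting". It expects those unrelated to the disease to stay stable. The first analysis is then "a series of paired t-tests to determine which markers significantly change between the two time points for patients". No covariate is attached to these tests.

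Smoking appears once in the analysis plan, near the end of Section 6.3, where "additional exploratory analyses will be examined to determine whether other patient level characteristics" are associated with the markers in general linear models. The examples given are gender, age and "smoking history (current/former/never"). The plan does not define a variable for change in smoking between visits, adjust the pre/post comparison for such a change, or repeat the comparison in patients whose smoking did not change. It also does not say which visit sets the smoking category.

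**The concern.** A paired comparison removes whatever is constant within a patient, including a long-standing smoking history. It does not remove something that differs between the two samples. If a patient smokes at the surgical consultation and not at four weeks, or the reverse, any marker that responds to tobacco can move for that reason alone. Section 6.3 would read that movement as association with lung cancer.

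The exploratory smoking term does not repair this. If the category is set before surgery, current smokers include both those who stop and those who continue. If it is set after surgery, former smokers include both recent and long-past quitters. Either way the term sits in a separate model and leaves the paired-test results as they were.

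What is at stake is the purpose that Section 6.1 gives for the marker analyses: ranking measures by effect size so that later studies know which to pursue. A tobacco marker placed high in that ranking is a false lead, and the data that would expose it will already have been collected.

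**Working it through.** **1. The plan's own figure.** Section 6.1 gives 90 patients, two-sided alpha 0.05 and 80% power for a difference of 0.30 SD. For a paired t-test with 89 degrees of freedom the noncentrality is 0.30 × √90 = 2.846 and the critical value is 1.987. Power is 80.4%, so the figure reproduces when the SD is taken as that of the within-patient change. The same scale is used below.

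**2. Inputs that must be assumed.** The documents give no share of smokers, no rate of stopping or starting, and no tobacco effect on any marker. Assume:
- one marker that is tobacco-sensitive and has no tumour effect;
- a fraction f of all 90 pairs (not of smokers only) changes status between samples;
- the marker shifts by δ in those patients, all in the same direction, and by 0 in the rest, where δ is in units of the SD of change within each group (set to 1).

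**3. Formulas.** Mean change = fδ. SD of change = √(1 + f(1 − f)δ²). Noncentrality = √90 × mean / SD. The chance of significance comes from the noncentral t distribution with 89 degrees of freedom.

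Worked case, f = 0.20 and δ = 1: mean 0.20; SD √(1 + 0.16) = 1.077; noncentrality 9.487 × 0.20 / 1.077 = 1.76; chance of significance 41%.

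**4. Results** (nominal rate 5%):

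| f (patients of 90) | δ = 0.5 | δ = 1 | δ = 2 |
|---|---|---|---|
| 5% (4.5) | 6% | 7% | 14% |
| 10% (9) | 7.5% | 15% | 36% |
| 20% (18) | 15% | 41% | 83% |

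A mean shift of 0.30, numerically the difference in the plan's power statement, arises for example when f = 0.20 and δ = 1.5 (0.20 × 1.5). The chance of significance is then 68%, below 80% because the mixture also inflates the SD.

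**5. Does adjustment work?** A simulation with 20,000 runs per scenario fixed the number of changers at 10% to 40% of 90 and used shifts of 0.5 to 1.5 SD. Testing the intercept of a model of change with a changed-status indicator gave rejection rates of 4.6% to 5.2%. The unadjusted test in the same simulation gave, for example, 14% at (10%, 1) and 41% at (20%, 1), in line with the formula.

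**6. Precision cost.** Restricting to unchanged patients leaves 81 pairs if 10% change status and 72 if 20% do. Intervals widen by √(90/81) = 1.054 and √(90/72) = 1.118, or about 5% and 12%. Power for 0.30 SD falls from 80% to 76% and 71%.

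**The case against.** The strongest reply is that the plan has already recognised the issue. Section 4.2.1 names tobacco as a possible confounder. The list of patient characteristics in Section 6.3 is open-ended, and its linear-model framework already takes change from before to after surgery as an outcome when it discusses stage. A model of change by smoking category would show part of a tobacco-driven shift, diluted by continuing smokers. This stands as far as it goes: the data collection is sound, and nothing forbids a change variable. But none is specified, and the paired tests would not be corrected by one that sits in a separate model. Where Section 6.3 wants a covariate examined at both time points and as a change, it says so, as it does for pulmonary function.

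It is also fair to say that few patients may change status. At the low end of the table the excess over 5% is trivial, and anyone who stopped before the consultation contributes nothing to this particular change. That is why the range has to be shown whole.

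Stronger readings are tempting and do not hold:
- A reader might infer that stopping smoking would mimic tumour removal in a known direction. The documents do not say which markers respond to tobacco or which way, and the planned test is two-sided.
- A reader might apply the percentages to the whole marker list. They describe one marker assumed to be tobacco-sensitive.
- A reader might conclude that the trial's findings would be wrong. The marker analyses are secondary and hypothesis-generating; the paired tests are described as a first analysis.

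**Conclusion.** The concern holds as a gap between data collection and analysis. Smoking is measured twice to identify confounding, yet the plan as written leaves a change in smoking between samples mixed with the effect of tumour removal. Under the stated assumptions (f from 5% to 20%, δ from 0.5 to 2), the chance that one tobacco-sensitive marker with no tumour effect reaches significance runs from about 6% to 83%. Where the study would fall in that range cannot be told from the documents. The upper end needs 18 of the 90 patients to change status and a shift of 2 SD in each.

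The consequence is a possibly distorted exploratory ranking. The primary feasibility proportions and their confidence intervals are unaffected. The change is worth making because it is cheap and puts the collected data to the use that Section 4.2.1 gives for them.

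**What to change.** Derive smoking change for each patient from the tobacco information at the two visits: unchanged, stopped, or started/resumed. State in Section 6.3 how each is defined.

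Keep the all-patient paired t-test. Beside it, report for each marker the change adjusted for smoking change, either as the intercept of a model of change with indicators for the changed groups or as the paired test in patients with unchanged status. Report how many patients fall in each group.

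In the ranking, flag any marker whose estimated change shrinks materially in the adjusted analysis. Do not rely on loss of significance alone, since the smaller sample can produce that by itself.

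**Cost.** One derived variable, one extra result per marker and no new data. The adjusted estimate is less precise: intervals about 5% to 12% wider, and power for 0.30 SD of about 76% or 71% instead of 80%, if 10% or 20% change status.

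**Limits.** The three groups do not capture patients who only cut down. Medication and diet, recorded for the same reason, are not dealt with by this step, so a marker that survives it is not thereby shown to be specific to lung cancer.
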